4.2.1.2 Body surface area

For missing BSA, the missing data will be imputed using LOCF as described in [Section 4.2.1.1](#) for the PASI score. This will also be presented using observed cases.

4.2.1.3 Investigator's Global Assessment

There will be no imputation of missing individual data for the IGA score. For the responder analysis, missing data will be imputed using NRI, ie, subjects with missing data at a specific visit will be considered as nonresponders for the analysis. This will include visits after the point of withdrawal or after the point of transition to the extension study, if applicable. In addition, IGA summaries will also be presented using observed cases.

4.2.1.4 Hospital Anxiety and Depression Scale

Missing data for the individual items of the HADS will be imputed as described in [Section 14.2](#) in order to calculate the HADS-A and HADS-D scores at each visit. No other imputation will be performed.

4.2.2 Safety laboratory data

Measurements below the limit of quantification (BLQ) will be imputed with half of the lower limit of quantification (LLOQ) for the purpose of calculating change from Baseline and for descriptive statistics. Measurements above the limit of quantification (ALQ), if applicable, will be imputed to the upper quantification limit.

These rules will be applied to all numeric safety laboratory data including clinical chemistry, hematology and urinalysis variables.

4.2.3 Bimekizumab concentration data

Measurements that are BLQ will be imputed with LLOQ/2 for the purpose of calculating the geometric mean and its 95% CI, the geoCV, the arithmetic mean, and SD for summaries and figures.

For the individual figures, any concentrations that are BLQ will be imputed with LLOQ/2, with the exception of predose BLQ measurements on Day 1 (Baseline Visit), which will be imputed with zero for linear scale plots.

Additional rules for PK data summaries are provided in [Section 9.1](#).

4.2.4 Dates and times

Partial dates may be imputed for the following reasons:

- Classification of AEs as treatment-emergent
- Classification of medications as past, prior or concomitant

Imputed dates will not be shown in the listings; all dates will be displayed as reported in the database.

The following rules will be applied for partial start dates:

- If only the month and year are specified and the month and year of first dosing is not the same as the month and year of the start date then use the 1st of the month, or the date of screening if this is later (if the latter imputation results in an end date that is earlier than the start date, then use the 1st of the month). If time is missing this will be imputed as 00:00 h;
- If only the month and year are specified and the month and year of first dosing is the same as the month and year of the start date, then use the date of first dosing. If this results in an imputed start date that is after the specified end date, then use the 1st of the month, or the date of screening if this is later (if the latter imputation results in an end date that is earlier than the start date, then use the 1st of the month). If the imputed date is the date of first dosing then time will be imputed with the time of the first injection (ie, event will be regarded as treatment-emergent);
- If only the year is specified, and the year of dosing is not the same as the year of the start date then use January 01 of the year of the start date. If time is missing this will be imputed as 00:00 h;
- If only the year is specified, and the year of dosing is the same as the year of the start date, then use the date of first dosing in the given year. If this results in an imputed start date that is after the specified end date, then use January 01 of the year of start date, or the date of screening if this is later (if the latter imputation results in an end date that is earlier than the start date, then use January 01). If the imputed date is the date of first dosing then time will be imputed with the time of the first injection (ie, event will be regarded as treatment-emergent);
- If the start date is completely unknown, then use the date of first dosing. If this results in an imputed start date that is after the specified end date, then use January 01 of the year of the end date, or the date of screening if this is later (if the latter imputation results in an end date that is earlier than the start date, then use January 01). If the imputed date is the date of first dosing then time will be imputed as the start time of the first injection (ie, event will be regarded as treatment-emergent).

The following rules will be applied for partial stop dates:

- If only the month and year are specified, then use the last day of the month;
- If only the year is specified, then use December 31 of the known year;
- If the stop date is completely unknown, do not impute the stop date

Missing or partially missing date and/or times will be imputed as described in [Table 4-1](#) for the calculation of duration of each AE. Adverse event duration is computed in and reported in day and time format: xx d hh:mm.

Table 4–1: Calculation rules for duration of adverse events

Data availability	Onset date/time	Outcome date/time	Calculation rules
Complete data	D1/T1	D2/T2	Duration = [(D2 – D1)*24 + (T2 – T1)]/24 d
End time missing	D1/T1	D2/--	End time is substituted by time 23:59h (=23.98 in decimal format) Duration = <[(D2 – D1)*24 + (23.98 – T1)]/24 d
Start time missing	D1/--	D2/T2	Onset time is substituted by time 00:00h Duration = <[(D2 – D1)*24 + T2]/24 d
Start and end time missing	D1/--	D2/--	Duration = <D2 – D1 + 1
Start day and time missing	--/--	D2/T2	Duration = <[(D2 – D0)*24 + (T2 – T0)]/24 d For a subject in the SS, D0 and T0 are the date and time of first administration of IMP and for screen failures, D0 is the date of the screening visit and T0 = 00:00h
End day and time missing	D1/T1	--/--	If the stop date is missing, duration will not be calculated.
Start and end date missing	--/--	--/--	If the stop date is missing, duration will not be calculated.

IMP=investigational medicinal product; SS=Safety Set.

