### Other medications

Subjects who are already receiving an established NSAID regimen (at least 8 weeks prior to Baseline) and have been on a stable dose for at least 4 weeks prior to Baseline may continue their use during the study. However, initiation of, or increase in dosage of, NSAIDs during the study (especially in subjects with a history of GI intolerance to NSAIDs or a history of GI ulceration) should be done with caution. Intra-articular steroid injections for arthritis of the knee are allowed.

Subjects who are already receiving an established anti-depressant regimen should be on a stable dose of anti-depressant for 12 weeks prior to Baseline.

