6.5.2 Prior medication definition

Prior medications include any medications that started prior to the date of administration of the first dose of IMP. This includes medications that started prior to dosing and continued after.

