6.5.3 Concomitant medication definition

Concomitant medications are medications taken at least 1 day in common with the study Treatment Period.

Any medication that started prior to dosing and continued after dosing will therefore be classified as both prior and concomitant. Such medications will therefore be counted in tabulations for both prior and concomitant categories.

Any medications with missing dates and/or times will be handled as described in [Section 4.2.4](#) in order to classify them as prior or concomitant.

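### The AE start-date rule is also applied to medications, so a drug with no recorded start date that is still in use at first dose is counted as concomitant but not prior

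*SAP*

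**What the plan says.** SAP 4.2.4 lists two purposes for imputing dates: "Classification of AEs as treatment-emergent" and "Classification of medications as past, prior or concomitant". One set of start-date rules follows, with no split between the two. For a missing start the rule is "If the start date is completely unknown, then use the date of first dosing". The clock time follows: "If the imputed date is the date of first dosing then time will be imputed as the start time of the first injection", and the stated consequence is that the "event will be regarded as treatment-emergent". The imputed start moves earlier only if it would otherwise fall after the end date. A completely unknown stop date is left unimputed.

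SAP 6.5.3 sends medications to these rules: "Any medications with missing dates and/or times will be handled as described in" SAP 4.2.4.

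The categories are defined in SAP 6.5.1 to 6.5.3. "Prior medications include any medications that started prior to the date of administration of the first dose of IMP", and SAP 6.5.2 adds that drugs continued after dosing are included. A concomitant drug shares at least one day with the Treatment Period. SAP 6.5.3 states that a drug begun before dosing and continued afterwards counts in both tables. SAP 6.5 plans separate tabulations for the two categories.

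**The concern.** Moving an unknown onset to the first dose is the cautious direction for an adverse event, because it keeps the event in the treatment-emergent tables. Medications have no equivalent reason. A drug whose start nobody recorded, and which was in use when the subject entered, may well have begun before the study. The rule nevertheless places its start at the first injection, and the prior-medication definition then excludes it.

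The protocol makes such drugs plausible. Section 7.8.1 permits continued use by "Subjects who are already receiving an established NSAID regimen (at least 8 weeks prior to Baseline"), and asks that antidepressants already in use be at a stable dose for 12 weeks before Baseline. If a drug known to have been established in this way has no recorded start, the rule classifies it wrongly.

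Adverse events also have an explicit override in SAP 11.2.1 where there is clear evidence of onset before dosing. SAP 6.5 contains no counterpart for medications. At stake is the completeness of one planned descriptive table.

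**Working it through.** The plan states no figure to reproduce, so the check applies the rules as written.

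1. SAP 4.2.4 and 6.5.3: medications with missing dates use the shared start-date rules.
2. SAP 4.2.4: unknown start → imputed start = date of first dose, at the time of the first injection.
3. SAP 6.5.2: prior requires start date < date of first dose. With start date = date of first dose, the test fails.
4. SAP 4.2.4: the earlier fallback needs an end date before the imputed start. An ongoing drug, or one with an unknown stop, has no such date. A stop on or after first dose does not meet the condition either.
5. SAP 6.5.3: the drug shares at least one day with the Treatment Period, so it is concomitant.

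Eight missing-date patterns were run through these rules with assumed dates (screening 25 October 2016, first dose 15 November 2016):

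| Recorded start | Recorded stop | Imputed start | Prior | Concomitant |
|---|---|---|---|---|
| Unknown | Ongoing | 15 Nov 2016 | No | Yes |
| Unknown | 1 Feb 2017 (after first dose) | 15 Nov 2016 | No | Yes |
| Unknown | 1 Sep 2016 (before screening) | 1 Jan 2016 | Yes (past) | No |
| Unknown | 1 Nov 2016 (screening to first dose) | 25 Oct 2016 | Yes (past) | No |
| Year only, dosing year | Ongoing | 15 Nov 2016 | No | Yes |
| Month and year only, dosing month | Ongoing | 15 Nov 2016 | No | Yes |
| Year only, earlier year | Ongoing | 1 Jan 2015 | Yes | Yes |
| Month and year only, earlier month | Ongoing | 25 Oct 2016 | Yes | Yes |

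The first row does not depend on the assumed dates: whatever the first-dose date, an undated ongoing drug is set equal to it and fails the strict inequality. The third and fourth rows show the fallback working when the drug stopped before first dose. The last two rows show that a recorded earlier year or month gives the intended double count. The clear defect is therefore confined to completely unknown starts with use on or after first dose, or with an unknown stop.

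**The case against.** Several points on the other side are sound. The drug is not lost: it stays in the concomitant table, and SAP 4.2.4 keeps imputed dates out of the listings. Entries on the psoriasis treatment history page are past by definition (SAP 6.5.1), so the Baseline summary of previous biologic use is unaffected. Protocol 7.8 requires dates of administration to be recorded, so a start with no year at all may be uncommon. The plan has no covariate adjustment (SAP 4.1) and no subgroups (SAP 4.10), so nothing inferential depends on the prior category.

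It can also be argued that SAP 4.2.4 says only that dates may be imputed, and that the data evaluation meeting in SAP 3.4 can settle missing values. That does not remove the problem. SAP 6.5.3 states without qualification that missing medication dates are handled under 4.2.4, and the rule there gives a definite answer. A general review meeting does not replace it.

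Two stronger readings are tempting. A reader might infer that an affected drug would look newly started on Day 1. The documents do not support this: the listings show dates as reported, and the Treatment Period table in SAP 6.5.4 counts use, whether the drug was ongoing or new. A reader might also infer that every permitted NSAID with an unknown start is misclassified. Protocol 7.8.1 contemplates NSAIDs being started during the study, so this follows only for a drug known to have been established before Baseline.

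The fifth and sixth rows of the table also lose prior status. For those partial dates, however, the earliest-date alternative would count some genuine on-study starts as prior. It exchanges undercounting for overcounting, so the direction is a matter of choice.

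**Conclusion.** The point holds for completely unknown start dates. Such a drug, if ongoing, with an unknown stop, or stopped on or after first dose, is counted as concomitant only. This contradicts the intent of SAP 6.5.2 and 6.5.3 for drugs begun before dosing and continued, and it undercounts the prior-medication table.

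The consequence is minor: one descriptive table in an exploratory study of about 45 subjects. The size of the undercount cannot be stated, because the documents do not say how many medication records lack a start date or how many of those drugs truly began before dosing. The conclusion rests only on reading the SAP rules literally.

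**What to change.** Keep the first-dose rule for adverse events. Add one sentence to SAP 4.2.4 or 6.5.3 for medications: a completely unknown start is treated as before first dose unless other recorded information shows that the drug began on study. The drug then counts as prior, and also as concomitant unless its stop date precedes first dose. Year-only or month-only starts that match the dosing year or month need not change.

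The cost is that sentence and one branch in the medication program. Concomitant counts stay the same, because the affected drugs already fall in the Treatment Period category of SAP 6.5.4 and would remain there. The downside is that an occasional on-study start with no recorded date would also appear as prior. SAP Section 1 calls for an amendment if definitions change before database lock; after lock, a supplementary table could be described in the clinical study report with its rationale.

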4.3 Handling of repeated and unscheduled measurements

All repeated and unscheduled measurements will be presented in the listings, where applicable. The following general rules will apply to all repeated and unscheduled measurements:

- For repeated or unscheduled measurements obtained prior to the first dose of IMP, the latest value (which may be scheduled or unscheduled) will be used in the calculation of descriptive statistics at each visit (ie, Screening and/or Baseline);
- For repeated or unscheduled measurements obtained at the designated Baseline visit, the latest value (which may be scheduled or unscheduled) will be defined as the Baseline provided that this occurred prior to the first dose of IMP;
- For repeated or unscheduled measurements obtained at any timepoint after the first dose of IMP, the first value will be used in the calculation of changes from Baseline and for the descriptive statistics (ie, in summaries by timepoint). Unscheduled and repeated measurements will not be included in the summaries by timepoint, for all timepoints after the first dose of IMP;
- Data from unscheduled visits may be used for tables that present abnormalities (where stated in the SAP amendment).

4.4 Handling of measurements obtained at the early withdrawal visit

Subjects who withdraw from the study prematurely will be encouraged to return for the EWD and the SFU Visit, the latter at 20 weeks following the final dose of IMP. The following rules will apply with regard to the inclusion of the results obtained at the EWD in the descriptive summaries:

- Any efficacy, PK, PD, immunological and safety measurements conducted at the EWD should be included in the summaries for the respective scheduled visit, if the EWD occurs at the time of the next scheduled visit (within the tolerance window specified in the protocol). For example, if the EWD occurs on Day 28, the results would be summarized together with the Week 4 results.
- If the EWD does not correspond to the day of a scheduled visit, the efficacy, safety and other relevant assessments of the EWD should be mapped to the nearest scheduled visit, relative to the Baseline visit date, following the last scheduled visit where assessments are available.
- If the date of the EWD is equidistant between 2 scheduled visits at which no scheduled assessments were performed, the assessments from the EWD will be mapped to the earliest of these visits.

For example, vital sign assessments are performed at Baseline, Weeks 2, 4, 8, 12, 16, 20, 24, 28 and 36. If a subject discontinues on Day 37, and the previous vital sign assessment was done at Week 4 (Day 28), the nearest scheduled assessment (following the last visit at which assessments were available) would be Week 8 (Day 56). Therefore, the EWD assessment should be re-assigned to the Week 8 visit.

However, if a subject discontinues at Day 37, and the previous vital sign assessment was done at Week 2 (Day 14), the EWD assessments would be re-assigned to the Week 4 (Day 28) visit, which would be the nearest scheduled visit relative to the Baseline visit date.

Different domains (eg, vital signs, ECG, safety laboratory tests, PASI, IGA) from the same EWD may be re-assigned to different study visits depending on the study schedule of assessments, ie, measurements obtained at the EWD can only be mapped to a scheduled visit at which the respective assessment was intended to be measured. Assessments from the EWD that are mapped to scheduled visits will be flagged in the data listings.

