**Table 5–1: Schedule of assessments**

Visit a / Week  Protocol activity	Screening b	Baseline	Treatment Period (Time after the first dose)								Wk 36 EWD/ SFU c	
			Wk 2	Wk 4	Wk 8	Wk 12	Wk 16	Wk 20	Wk 24	Wk 28		
Blood sample for bimekizumab plasma concentrations n		X	X	X	X	X	X	X	X	X	X	X
Blood sample for anti-bimekizumab antibodies n		X		X	X	X	X	X	X	X	X	X
Blood sample for cytokines, complement, candidate biomarker analysis, and flow cytometry n		X			X	X	X					X
Blood sample for RNA, proteins, and metabolites biomarkers n	X	X			X	X	X				X	X
Skin biopsy o		X (2)			X (2)			X (1)			X (1)	
PASI	X	X	X	X	X	X	X	X	X	X	X	X
IGA	X	X	X	X	X	X	X	X	X	X	X	X
BSA affected by psoriasis	X	X	X	X	X	X	X	X	X	X	X	X
Concomitant medication	X	X	X	X	X	X	X	X	X	X	X	X
Adverse events	X	X	X	X	X	X	X	X	X	X	X	X
IXRS	X	X		X				X				
Subject identification card	X											
Bimekizumab or placebo administration		X		X				X				

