### **8.12 Early Withdrawal Visit**

Subjects withdrawing early from the study (see [Section 6.3](#)) should undergo the same assessments scheduled for the Week 36 Visit (see [Section 8.11](#)) as soon as possible after withdrawal (as an Early Withdrawal Visit) and then enter the SFU Period, completing study participation with the SFU Visit (Week 36 Visit assessments again) 20 weeks after their last dose of study medication.

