9.2 Pharmacodynamics

The results of the PD assessments (flow cytometry variables) will be listed by treatment group and subject (based on the SS) including changes from Baseline.

Absolute values and changes from Baseline will be summarized (including 95% CI) by treatment group based on the PD-PPS.

Figures of mean and mean changes from Baseline (including 95% CI) will be presented with separate plots for each variable and both treatment groups overlaid on the same plot.

The list of flow cytometry variables to be measured is provided in [Section 14.3](#).

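### After Week 16, SAP 4.4 files early-withdrawal flow-cytometry and ECG results under Week 36 (or back under Week 16) with no distance limit and no rule for a clash with the follow-up visit

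*SAP*

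**What the plan says.** SAP 4.4 first places an EWD result with a scheduled visit if it falls inside that visit's protocol window. Otherwise the result is "mapped to the nearest scheduled visit, relative to the Baseline visit date, following the last scheduled visit where assessments are available". The tie rule begins "If the date of the EWD is equidistant between 2 scheduled visits at which no scheduled assessments were performed" and chooses the earlier visit. The section ends with the restriction that "measurements obtained at the EWD can only be mapped to a scheduled visit at which the respective assessment was intended to be measured". No maximum distance is given. The only stated safeguard there is a flag in the listings.

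The Protocol Table 5–1 row "Blood sample for cytokines, complement, candidate biomarker analysis, and flow cytometry" and the visit lists in Protocol 8.2 to 8.11 place flow cytometry at Baseline, Weeks 8, 12 and 16, and Week 36/SFU. They place the ECG at Screening, Baseline, Weeks 4 and 16, and Week 36/SFU. Neither is listed at Weeks 20, 24 or 28.

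Protocol 8.12 gives a withdrawing subject an EWD visit with the Week 36 assessments, followed by the SFU, "completing study participation with the SFU Visit (Week 36 Visit assessments again) 20 weeks after their last dose of study medication".

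For repeated or unscheduled values after the first dose, SAP 4.3 says "the first value will be used in the calculation of changes from Baseline and for the descriptive statistics", and it leaves repeats out of the by-visit summaries.

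Two sets of outputs use these labels. For flow cytometry, SAP 9.2 says "Absolute values and changes from Baseline will be summarized (including 95% CI) by treatment group based on the PD-PPS". SAP 11.4.3 tabulates ECG values, changes and QTcF categories by arm and visit.

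**The concern.** The mapping rule suits PASI and vital signs, which have a visit every two to four weeks up to Week 28. For an assay with a 20-week gap in its schedule, the same rule moves a result a long way and the table gives no sign of it.

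The gap sits where it matters most for flow cytometry. This is the only pharmacodynamic (PD) variable in the tables (SAP 2.2.3.2). The Week 16 sample is drawn before dosing (Protocol 8.7), so Week 36 is the only scheduled flow-cytometry timepoint after the two regimens diverge. A result taken at Week 20 but labelled Week 36 enters the one by-arm comparison that could show a difference.

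For QTcF, the categories are tabulated by visit only. Laboratory and vital-sign abnormalities also have an all-visits row (SAP 11.3, 11.4.1); none is stated for ECG. A QTcF value that lost its place in the Week 36 row would appear only in the listing.

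**Working it through.** **Inputs.** Candidate visits are those at which the assay is scheduled and that come after the last visit with data (SAP 4.4). Day number is 7 × week, as in the SAP's own examples (Week 4 is Day 28). The rule picks the smallest |7 × week − EWD day|, with ties going to the earlier visit. After Week 16 the schedules are: flow cytometry and ECG, Week 36 only; vital signs, Weeks 20, 24, 28 and 36.

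**Reproducing the SAP's examples (vital signs).**
- EWD on Day 37, last assessment Week 4: the nearest later visit is Week 8 (|56 − 37| = 19). The SAP says Week 8.
- EWD on Day 37, last assessment Week 2: |28 − 37| = 9 against |56 − 37| = 19, so Week 4. The SAP agrees: "the EWD assessments would be re-assigned to the Week 4 (Day 28) visit".
- EWD on Day 28: Week 4, as in the SAP.

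**Case 1: Week 16 flow cytometry or ECG available.** Week 36 (Day 252) is the only candidate, so every EWD from Day 113 to Day 251 goes there.

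| EWD at | Day | Flow/ECG filed as | Days early (252 − day) | Vital signs filed as |
|---|---|---|---|---|
| Day after Week 16 | 113 | Week 36 | 139 | Week 20 |
| Week 20 | 140 | Week 36 | 112 | Week 20 |
| Week 24 | 168 | Week 36 | 84 | Week 24 |
| Week 28 | 196 | Week 36 | 56 | Week 28 |

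The largest shift is 139/7 = 19.9 weeks.

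**Case 2: Week 16 result missed.** Candidates are Week 16 (Day 112) and Week 36 (Day 252). The midpoint is (112 + 252)/2 = Day 182, and the tie goes to the earlier visit.
- EWD on Days 113 to 182: filed back to Week 16, up to 182 − 112 = 70 days late.
- EWD on Days 183 to 251: filed to Week 36.

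If the Week 16 dose was given although the assessment was missed, Case 2 puts a post-dose result into a row that otherwise holds predose results.

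**When two results meet at Week 36.** The SFU is due at last-dose week + 20: 16 + 20 = Week 36, but 4 + 20 = Week 24 and 0 + 20 = Week 20. A true Week 36 result to compete with the mapped one therefore exists only if the subject was dosed at Week 16, withdrew later, and attended the SFU. SAP 4.4 has no rule for that pair. The nearest text, SAP 4.3, would keep the earlier value, which is the EWD result.

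**Weight of one result.** At full attendance, one subject is 1/15 = 6.7% of the arm B mean and 1/30 = 3.3% of the arm A mean.

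**The case against.** **SAP 4.3 does not name an EWD/SFU pair.** It governs repeated and unscheduled measurements, and the SFU is a scheduled visit. The tie rule in SAP 4.4 speaks of visits where nothing was performed, which suggests that EWD results are meant to fill empty visits. A reader might infer that the SAP discards the true Week 36 value; the documents do not say so. What stands is that no explicit rule exists and that the closest one points to the wrong value.

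**Not every late EWD result goes to Week 36.** A reader might infer that all of them do. Case 2 shows otherwise, and the SAP's second example supports mapping back to a missed visit.

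**The window bullet could rescue a Week 20 EWD.** The first bullet of SAP 4.4 names PD and would place it in the Week 20 summary. The closing restriction forbids this for an assay not scheduled at Week 20, so at best the section conflicts with itself.

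**There is a review step.** The data evaluation meeting (SAP 3.4) can decide how to handle withdrawals and visit-schedule deviations before unblinding, and mapped values are flagged in listings. This allows case-by-case repair but does not change the rule that builds the by-visit tables.

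**Drug level is not PD effect.** With a half-life of about 28 days (Protocol 2.2.1) and log-linear decline, a Week 20 sample has 2^(16/4) = 16 times the drug level of a Week 36 sample. A reader might infer a biased Week 36 PD mean of similar size. The outputs are cell-subset percentages and ECG intervals, and the documents give no link from concentration to either. In arm A the last active dose is at Week 4, so by Week 20 about 2^(−4) = 6% of the level would remain. The ratio shows that the label is wrong, not by how much the mean shifts.

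**Conclusion.** The point holds in a limited form. With a Week 16 result in hand, SAP 4.4 as written labels any later EWD flow-cytometry or ECG result as Week 36, up to 139 days early. Without one, it labels results up to Day 182 as Week 16, up to 70 days off. Where a Week 16 dose and an attended SFU produce a second Week 36 result, the plan does not say which to use.

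The damage is confined to descriptive by-arm Week 36 (or Week 16) flow-cytometry and ECG/QTcF summaries. PASI, IGA, BSA and vital signs are scheduled at Weeks 20, 24 and 28, so the primary endpoint is not affected.

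The number of affected subjects is not stated. If 5 to 15% of the 45 subjects withdrew early (an assumption), that would be 2.25 to 6.75, or about 2 to 7. Only those withdrawing after Week 16 count here, so the relevant number is no larger. Relapsers who leave for the extension study are counted as completers (SAP 5.1) and are not in this group. No bias of a given size in any mean has been shown.

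These figures rest on the SAP's day numbering and on reading its closing restriction literally. A change is worthwhile because it is cheap and protects the only flow-cytometry timepoint after the arms diverge.

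**What to change.** Amend SAP 4.4 as follows:
- Map an EWD result to a scheduled visit only if it falls within a pre-specified maximum window of that visit's nominal day. The documents give no basis for a particular width, so the sponsor should choose and state one.
- Show any EWD result outside the window in a separate early-withdrawal row and in the listing.
- State that a result obtained at a performed scheduled visit or SFU takes precedence over a mapped EWD result for the same visit, whatever SAP 4.3 says about first values.
- Apply the same rule to flow-cytometry and ECG results from the SFU assessments done at extension entry (Week 20, 24 or 28). SAP 2.3 requires those assessments, but SAP 4.4 covers only the EWD and leaves their visit label undefined.

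The cost is a few sentences, a visit-window variable in the analysis datasets, and a slightly smaller n at Week 36. No new data are needed. Under SAP Section 1, a change of definition before database lock goes into a further SAP amendment.
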